#### **Measurable Disease**

Measurable lesions are defined as those that can be accurately measured in at least one dimension (longest diameter to be recorded) as  $\geq 20$  mm with conventional techniques (CT, MRI, x-ray) or as  $\geq 10$  mm with spiral CT scan. All tumor measurements must be recorded in millimeters (or decimal fractions of centimeters).

#### **Non-Measurable Disease**

All other lesions (or sites of disease), including small lesions (longest diameter  $< 20$  mm with conventional techniques or  $< 10$  mm using spiral CT scan), are considered non-measurable disease. Bone lesions, leptomeningeal disease, ascites, pleural/pericardial effusions, lymphangitis cutis/pulmonis, inflammatory breast disease, abdominal masses (not followed by CT or MRI), and cystic lesions are all non-measurable.

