#### **4.1 Eligibility Inclusion Criteria**

1. Male or female, age  $\geq$ 18 years with HCC refractory to currently available therapies.
2. Documented HCC by pathologic criteria.

Recommendations for diagnosis of HCC have been issued in a guideline from the American Association for the Study of Liver Diseases, which can be accessed through the AASLD web site at <http://www.aasld.org/practiceguidelines/Pages/default.aspx>.

3. Subject must be able to give written informed consent and be able to follow protocol requirements
4. Life expectancy greater than 3 months
5. Be Child's-Pugh class A or B
6. ECOG Performance status of  $\leq 2$
7. If female of childbearing potential must have negative pregnancy test at screening and may not be breast-feeding
8. Females of child-bearing potential (< one year post-menopausal with documented FSH greater than 30 IU/L or surgically not sterile), must agree to practice an effective method of avoiding pregnancy (including oral or implanted contraceptives, intrauterine device, condom, diaphragm with spermicidal, cervical cap, abstinence or sterile sex partner) from the time informed consent is signed through follow-up. Males must agree to take appropriate precautions to avoid fathering a child from screening through follow-up.
9. No other active malignancy requiring treatment in the last 3 years other than adequately treated non-melanomatous skin cancer, adequately treated cervical carcinoma in-situ, superficial adequately treated bladder cancer or prostatic intraepithelial neoplasia without evidence of prostate cancer.
10. Adequate bone marrow, liver and renal function as assessed by the following:
  - Hemoglobin  $\geq 8$  g/dL
  - WBC  $\geq 4,000$ /uL
  - Absolute neutrophil count  $\geq 1,500$ /uL
  - Platelets  $\geq 75,000$ /uL
  - Total bilirubin  $\leq 1.5$  times ULN
  - ALT and AST  $\leq 5$  times ULN
  - Creatinine  $\leq 1.5$  times ULN
  - Albumin  $\geq 2.5$  mg/dL
11. Subjects who have received previous radiotherapy, loco-regional, or systemic therapy are eligible. A minimum interval of 4 weeks since the last anti-cancer treatment of any kind is required.
12. Subjects with brain metastases or a history of previously treated brain metastasis are eligible but must:
  - Have been treated by surgery or stereotactic radiosurgery (SRS) at least 4 weeks prior to enrollment

- AND have a baseline MRI or CT that shows no evidence of active intracranial disease

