#### **4.2 Exclusion Criteria**

1. Any concurrent active malignancy requiring treatment (other than basal or squamous cell carcinoma of the skin, carcinoma in situ of the cervix, superficial bladder tumors, or other malignancies curatively treated > 3 years prior to study entry)
2. History of severe cardiovascular disease within the last 12 months: symptomatic congestive heart failure, myocardial infarction, coronary artery disease (CAD), life threatening arrhythmias, uncontrolled hypertension
3. Renal failure requiring hemo- or peritoneal dialysis
4. Unstable systemic diseases or active uncontrolled infection
5. Known history of HIV infection
6. Clinically significant gastrointestinal bleeding within 30 days prior to study entry
7. Major surgery, open biopsy or significant traumatic injury within 4 weeks prior to study entry
8. Child's-Pugh Class C
9. Any malabsorption problem that, in the investigator's opinion, would prevent adequate absorption of the study drug
10. Presence of any other medical complications that in the investigator's opinion, suggests a survival of < 3 months
11. Substance abuse, or medical, psychological or social conditions that may interfere with the patient's participation in the study or evaluation of the study results
12. Patient inability to swallow oral medications
13. Any condition that is unstable or which could jeopardize the safety of the patient and his/her compliance in the study
14. Pregnant or breast-feeding patients
15. Being of reproductive potential and unable or unwilling to practice an effective contraceptive method

16. Lack of positive staining for RB-function on tumor biopsy.

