#### **Non-Target Lesions**

All other lesions (or sites of disease) should be identified as **non-target lesions** and should also be recorded at time of disease recurrence. Non-target lesions include measurable lesions that exceed the maximum numbers per organ or total of all involved organs as well as non-measurable lesions. Measurements of these lesions are not required but the presence or absence of each should be noted throughout follow-up.

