## **6.2 Response Assessment**

Response is assessed on the basis of clinical, radiological, and pathological criteria. Standard imaging via MRI and/or CT scan will be used for evaluation of nodal disease based on RECIST criteria. These techniques should be performed with cuts of 10 mm or less in slice thickness contiguously. Spiral CT should be performed using a 5 mm contiguous reconstruction algorithm.

The subject's response will be assessed based on the response of the target lesions, the response of non-target lesions and the presence or absence of new lesions through out the course of the study.

Response Criteria for Target Lesions:

Complete Response (CR)	Disappearance of all target lesions
Partial Response (PR)	At least 30% decrease in the sum of the LD of target lesions, taking as reference the baseline sum LD
Progressive Disease (PD)	At least 20% increase in the sum of the LD of target lesions, taking as reference the smallest sum LD recorded since the treatment started or the appearance of one or more new lesions.
Stable Disease (SD)	Neither sufficient shrinkage to qualify for PR nor sufficient increase to qualify for PD, taking as reference the smallest sum LD recorded since the treatment started

Response Criteria for Non-target Lesions

Complete Response (CR)	Disappearance of all non-target lesions and normalization of tumor marker level
Incomplete Response/Stable Disease (SD)	Persistence of one or more non-target lesions and or maintenance of tumor marker above normal limits.
Progressive Disease (PD)	Appearance of one or more new lesions and or unequivocal progression of existing non target lesions

Subjects with global deterioration in health status requiring discontinuation of treatment without objective evidence of disease progression will be classified as having symptomatic deterioration. Every effort will be made to document objective progression.

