## 7.0 Endpoints:

### 7.1 Primary Endpoint

#### Time to Progression (TTP)

Progression-free survival (PFS) is the time elapsed between treatment initiation and tumor progression or death from any cause, with censoring of patients lost to follow up. Time to

Progression (TTP) is defined by the FDA as the time from subject randomization until tumor progression is documented. Time to treatment failure (TTF) is a composite endpoint defined as the time from randomization until the patient stops trial treatment for any reason including progression, adverse events, insufficient therapeutic response, death, failure to return, and refused treatment/did not cooperate/withdrew consent. PFS assumes that patient deaths are randomly related to tumor progression. Compared to TTP, PFS is the preferred regulatory endpoint however in situations where deaths may be unrelated to cancer such as in patients with HCC and cirrhosis, TTP is an acceptable endpoint. In this study, TTP will be defined as the date of enrollment on trial to the first observation of disease progression, as classified by modified RECIST (Version 1.1) or clinical progression. The date of last dose of treatment or death will be used as the date of this event in the case that recurrent disease was not assessable. An interim analysis for futility will be conducted after the first 10 events have occurred. The probability of a significant final result given the observed data at the time of the interim analysis (i.e., the conditional power) will be estimated (Lachin 2005). The study will be stopped for futility if the conditional power is less than 60%. That is, the study will be stopped if there is a preponderance of evidence that completion will not yield a significant result.

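### Ascites and effusions count as disease under section 6.1 without evidence of tumour involvement, so fluid caused by cirrhosis can be scored as progression in the primary TTP endpoint

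*Combined protocol and SAP*

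**What the plan says.** All references are to the combined protocol and SAP.

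- **6.1, Non-Measurable Disease.** The category opens with "All other lesions (or sites of disease), including small lesions" and then names "Bone lesions, leptomeningeal disease, ascites, pleural/pericardial effusions, lymphangitis cutis/pulmonis, inflammatory breast disease", among others. No malignancy or cytology condition is attached to ascites or effusions.
- **6.1, Non-Target Lesions.** "Non-target lesions include measurable lesions that exceed the maximum numbers per organ or total of all involved organs as well as non-measurable lesions". Their presence or absence is to be noted throughout follow-up.
- **6.2, non-target criteria.** PD is "Appearance of one or more new lesions and or unequivocal progression of existing non target lesions". Persistence of any non-target lesion rules out a complete response (CR).
- **7.1.** TTP runs from enrollment "to the first observation of disease progression, as classified by modified RECIST (Version 1.1) or clinical progression". The section prefers TTP here because "in situations where deaths may be unrelated to cancer such as in patients with HCC and cirrhosis, TTP is an acceptable endpoint".
- **4.1 and 4.2.** Patients must "Be Child's-Pugh class A or B". The liver-function exclusion is "Child's-Pugh Class C"; ascites is not an exclusion.
- **3.0.** Tumour response is assessed by the investigator. No central review is described.

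**The concern.** The list in 6.1 is general solid-tumour wording (it includes inflammatory breast disease) and has not been adapted to a cirrhotic population. In a patient with Child-Pugh B cirrhosis, ascites may reflect the liver disease alone. No step from 6.1 to 7.1 asks which it is.

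The primary endpoint is at stake. Section 7.1 chose TTP because deaths in HCC with cirrhosis may be unrelated to cancer. A response rule that can count a complication of cirrhosis as progression works against that reason. Each such event shortens TTP without tumour growth and so costs power. It also brings the 10-event futility look forward and tends to lower the conditional power found there. Benign ascites persisting from baseline could also block a CR.

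**Working it through.** **Step 1: the route into the endpoint.** Fluid is non-measurable disease (6.1), hence non-target disease (6.1). Its appearance or unequivocal increase is PD (6.2), and PD is the TTP event (7.1). The word unequivocal applies only to existing non-target lesions; the appearance limb has no such threshold. No section requires fluid to be attributed to tumour before PD is called.

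**Step 2: reproduce the sample size.** Section 11.0 gives a median of 24 against 12 weeks, alpha 0.05 (sidedness not stated), power 90% and 19 evaluable patients. For a single-arm exponential test, events = (z_alpha + z_power)² / [ln(24/12)]².

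- One-sided: (1.645 + 1.282)² / 0.693² = 17.8, so 18 events.
- Two-sided: (1.960 + 1.282)² / 0.693² = 21.9, so 22 events.

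The stated 19 is close to the one-sided result, with every patient followed to an event. The exact power with 19 events is P(χ²₃₈ > 53.38 × 12/24) = P(χ²₃₈ > 26.69) = 91.6%, where 53.38 is the upper 5% point of χ²₃₈.

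**Step 3: add benign fluid as an event.** The documents give no rate of non-malignant ascites or effusion, so q, the probability by week 24, is an assumption. Hazards are taken as constant, fluid as independent of tumour progression, and every fluid event as called PD.

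- Tumour progression hazard: ln 2 / 24 = 0.02888 per week
- Fluid hazard: h = −ln(1 − q) / 24
- Measured median: m = ln 2 / (0.02888 + h)
- Power: P(χ²₃₈ > 53.38 × 12/m)
- Share of events that are not cancer: h / (0.02888 + h)

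| q (assumed) | h per week | Measured median, weeks | Share not cancer | Power, 19 events |
|---|---|---|---|---|
| 0 | 0 | 24.0 | 0% | 91.6% |
| 5% | 0.00214 | 22.3 | 7% | 86% |
| 10% | 0.00439 | 20.8 | 13% | 79% |
| 20% | 0.00930 | 18.2 | 24% | 60% |

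If only half of a 5% rate were called PD (q = 2.5%), the median would be 23.2 weeks and power 89%, close to plan.

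**The case against.** A reader might infer that the protocol scores liver decompensation as cancer progression. The documents do not support that.

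- **The text permits this scoring but does not direct it.** The list falls under lesions or sites of disease, and 6.1 elsewhere speaks of tumour lesions. An assessor may read it as classifying fluid already judged to be tumour. Section 6.2 also says response rests on clinical, radiological and pathological criteria, so pathology may be used. This stands, but it leaves the call to one investigator's reading in an open-label trial. The modified RECIST 1.1 that governs is not described, so it cannot be shown to supply the safeguard.
- **The rule reaches only ascites and effusions.** Other forms of decompensation could enter TTP through the undefined clinical progression, or through the use of last dose or death as the event date when recurrence is not assessable (7.1). Those are separate problems, which a change to 6.1 would not close.
- **Section 7.1 speaks of deaths, not of all cirrhosis events.** The rule therefore sits badly with the stated rationale but does not formally contradict it.
- **The size is assumed, and the direction is conservative.** Calling every benign fluid event PD puts the loss at its upper end for a given rate. Extra events work against a false claim of benefit. If the historical 12-week figure counted fluid the same way, the comparison may be little affected; the documents do not say.

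These points limit the claim. They do not close the route set out in step 1.

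**Conclusion.** The concern holds in limited form. Section 6.1 requires no evidence of tumour involvement for ascites or effusions, so new or clearly increased fluid caused by cirrhosis can become a primary TTP event in a trial that admits Child-Pugh B. The likely effect is a shorter measured TTP and lower power, subject to how the historical series treated fluid.

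The tabulated losses are illustrations, not estimates. They rest on assumed rates, constant and independent hazards, every fluid event being called PD, a one-sided 5% test and 19 observed events. At low rates, or with selective calling, the loss is small. The definition should still be corrected, because the rule as written can produce a wrong event in a very small trial and the correction is cheap.

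**What to change.** Add to 6.1 and 6.2, for endpoint classification: ascites and pleural or pericardial effusions count as disease, and their appearance or increase as progression, only with documented evidence of tumour involvement (for example, cytology already obtained in routine care). Otherwise they are not used for CR, stable disease or PD. They are reported as adverse events only as 9.1 and 9.2 already require, so stable pre-existing ascites does not become an adverse event.

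Add a sensitivity analysis of TTP with fluid-only progressions counted the other way, and record their dates so that it can be run.

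PD also ends treatment under 3.0, the Treatment Schedule in 5.0 and 5.6. The sponsor should reconcile those sections with the revised endpoint definition; this review takes no position on the treatment rule itself.

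The cost is a short definition, one data field and one extra analysis, with no added procedure, scan or patient. One small downside: a malignant effusion that is never sampled would be dated later, from other lesions.

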#### **Target Lesions**

All measurable lesions up to a maximum of five lesions per organ and ten lesions in total, representative of all involved organs, should be identified as **target lesions** and recorded and measured at baseline. Target lesions should be selected on the basis of their size (lesions with the longest diameter) and their suitability for accurate repeated measurements (either by imaging techniques or clinically). A sum of the longest diameter (LD) for all target lesions will be calculated and reported at time of disease recurrence.

#### **Non-Target Lesions**

All other lesions (or sites of disease) should be identified as **non-target lesions** and should also be recorded at time of disease recurrence. Non-target lesions include measurable lesions that exceed the maximum numbers per organ or total of all involved organs as well as non-measurable lesions. Measurements of these lesions are not required but the presence or absence of each should be noted throughout follow-up.

## **6.2 Response Assessment**

Response is assessed on the basis of clinical, radiological, and pathological criteria. Standard imaging via MRI and/or CT scan will be used for evaluation of nodal disease based on RECIST criteria. These techniques should be performed with cuts of 10 mm or less in slice thickness contiguously. Spiral CT should be performed using a 5 mm contiguous reconstruction algorithm.

The subject's response will be assessed based on the response of the target lesions, the response of non-target lesions and the presence or absence of new lesions through out the course of the study.

Response Criteria for Target Lesions:

Complete Response (CR)	Disappearance of all target lesions
Partial Response (PR)	At least 30% decrease in the sum of the LD of target lesions, taking as reference the baseline sum LD
Progressive Disease (PD)	At least 20% increase in the sum of the LD of target lesions, taking as reference the smallest sum LD recorded since the treatment started or the appearance of one or more new lesions.
Stable Disease (SD)	Neither sufficient shrinkage to qualify for PR nor sufficient increase to qualify for PD, taking as reference the smallest sum LD recorded since the treatment started

Response Criteria for Non-target Lesions

Complete Response (CR)	Disappearance of all non-target lesions and normalization of tumor marker level
Incomplete Response/Stable Disease (SD)	Persistence of one or more non-target lesions and or maintenance of tumor marker above normal limits.
Progressive Disease (PD)	Appearance of one or more new lesions and or unequivocal progression of existing non target lesions

Subjects with global deterioration in health status requiring discontinuation of treatment without objective evidence of disease progression will be classified as having symptomatic deterioration. Every effort will be made to document objective progression.

## 7.0 Endpoints:

### 7.1 Primary Endpoint

#### Time to Progression (TTP)

Progression-free survival (PFS) is the time elapsed between treatment initiation and tumor progression or death from any cause, with censoring of patients lost to follow up. Time to

Progression (TTP) is defined by the FDA as the time from subject randomization until tumor progression is documented. Time to treatment failure (TTF) is a composite endpoint defined as the time from randomization until the patient stops trial treatment for any reason including progression, adverse events, insufficient therapeutic response, death, failure to return, and refused treatment/did not cooperate/withdrew consent. PFS assumes that patient deaths are randomly related to tumor progression. Compared to TTP, PFS is the preferred regulatory endpoint however in situations where deaths may be unrelated to cancer such as in patients with HCC and cirrhosis, TTP is an acceptable endpoint. In this study, TTP will be defined as the date of enrollment on trial to the first observation of disease progression, as classified by modified RECIST (Version 1.1) or clinical progression. The date of last dose of treatment or death will be used as the date of this event in the case that recurrent disease was not assessable. An interim analysis for futility will be conducted after the first 10 events have occurred. The probability of a significant final result given the observed data at the time of the interim analysis (i.e., the conditional power) will be estimated (Lachin 2005). The study will be stopped for futility if the conditional power is less than 60%. That is, the study will be stopped if there is a preponderance of evidence that completion will not yield a significant result.

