### **2.2 Study Endpoints:**

1. Time to disease progression (TTP) defined as time from enrollment on study to documented progression of disease.
2. Safety and Tolerability including adverse events, and significant laboratory abnormalities

3. Overall survival (OS) defined as the time from entry on trial to the time of death, from any cause.
4. Objective Response Rate defined as the proportion of subjects with either a confirmed CR or a confirmed PR as determined using modified RECIST (Version 1.1) criteria

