### **3.0 Study Design**

This is an open-label non-randomized single-institution study for subjects with inoperable, recurrent/refractory advanced hepatocellular carcinoma (HCC). Subjects must have failed or be intolerant of standard first line therapy, sorafenib (Nexavar®). Eligible subjects will receive 125 mg PD-0332991 capsules orally once daily, administered days 1-21 of a 28-day cycle, in repeated cycles.

Subjects will be permitted to receive protocol directed therapy until disease progression by modified RECIST (Version 1.1) (Response Evaluation Criteria in Solid Tumors) guidelines or clinical progression, unacceptable toxicity, withdrawal of consent or death. Tumor response assessment will be performed by the Investigator and will consist of evaluation by CT or MRI using modified RECIST (Version 1.1) guidelines every 8 weeks. Subjects who discontinue therapy for disease progression or other reasons will be followed for safety on Day 28 ( $\pm$  3 days), Day 56 ( $\pm$  3 days) and every 3 months thereafter or until death, from the last administration of protocol –directed therapy.

Subjects will be continuously assessed for evidence of acute and cumulative toxicity. Vital signs, Physical examinations, performance status, laboratory safety tests will be obtained and assessed prior to drug administration and at regular intervals throughout the study. Toxicity will be evaluated every 2 weeks during the first 3 cycles and thereafter monthly (once per cycle) by the Investigator according to National Cancer Institute (NCI) Common Terminology Criteria for Adverse Events (CTCAE), Version 4.0 (which can be viewed on-line at the following NCI web site: <http://ctep.cancer.gov/reporting/ctc.html>).

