### **Overall Survival**

Overall survival (OS) is measured from the entry onto a trial until death of any cause. Date and cause of death will be recorded. The cause of death will be categorized as either cancer-related or cancer-unrelated.

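### Section 7.1 dates the TTP event at last dose or death when disease was not assessable, without requiring that progression had been judged present, and no TTP censoring rule is given

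*Combined protocol and SAP*

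**What the plan says.** Section 2.2 defines the primary endpoint by documented progression only: "Time to disease progression (TTP) defined as time from enrollment on study to documented progression of disease". Section 7.1 widens this to progression by modified RECIST or clinical progression, and adds a fallback rule for dating: "last dose of treatment or death will be used as the date of this event in the case that recurrent disease was not assessable".

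The same section describes two other endpoints as different from TTP. PFS runs to "tumor progression or death from any cause, with censoring of patients lost to follow up". Time to treatment failure runs "until the patient stops trial treatment for any reason including progression, adverse events, insufficient therapeutic response, death" and further reasons. TTP is preferred to PFS because "in situations where deaths may be unrelated to cancer such as in patients with HCC and cirrhosis, TTP is an acceptable endpoint".

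Section 7.1 also ties the futility look to the event count: "An interim analysis for futility will be conducted after the first 10 events have occurred". Under overall survival, section 7.2 records why patients died: "The cause of death will be categorized as either cancer-related or cancer-unrelated". Section 11.1 names Kaplan-Meier for TTP and states no censoring rule.

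**The concern.** The only condition on the fallback is that disease was not assessable. That term is not defined, and the text does not say which of the two dates applies when a patient has both. Nothing limits the fallback to patients in whom progression had been concluded. The only mention of censoring in section 7.1 belongs to its description of PFS. The TTP status of a patient who dies without progression, stops for toxicity, withdraws, is lost, or is progression-free at cutoff is therefore not stated.

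Two analysts with the same data could count different events among 19 evaluable patients. Under the literal reading the endpoint becomes partly PFS and partly time to treatment failure, and the deaths that motivated TTP come back in as events. The result is then compared with a figure that section 11.0 calls a median TTP. The same event count triggers the futility look.

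A related gap: section 3.0 lets treatment run until progression by RECIST "guidelines or clinical progression, unacceptable toxicity, withdrawal of consent or death", so clinical progression is kept apart from toxicity and death. Section 6.2 has a category of symptomatic deterioration without objective progression, but does not say whether it is clinical progression and hence a TTP event.

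**Working it through.** **The two readings, by type of patient**

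| Patient | Dating-only reading | Literal reading |
|---|---|---|
| Progression judged present, date not obtainable from imaging | Event at last dose or death | Same |
| Dies, no progression seen, disease not assessed | Not an event; censoring date not stated | Event at death |
| Stops drug, no later scan | Not an event; censoring date not stated | Event at last dose |
| Progression-free at cutoff | Not stated | Not stated |

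The readings differ in rows two and three. The missing censoring rule matters under both.

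**The plan's own figure.** Inputs from section 11.0: median 24 against 12 weeks, alpha 0.05, power 90%, 19 evaluable patients. Sidedness is not stated; the 90% intervals in section 11.1 match a one-sided 5% test. One-sample exponential formula: events = (1.645 + 1.282)² / (ln 2)² = 17.8, so 18. With 19 events the exact test gives 91.6% power. The stated 19 is consistent with this and is not disputed. (Two-sided 5% would need 22 events; 19 would give 87.0%.)

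**Illustration of the literal reading.** Assumptions not in the documents: exponential times, true median 24 weeks, continuous observation, all 19 followed to progression or exit, exits independent of progression, no interim look, no week-8 filter. Let s be the share of counted events that are not progression, r = s/(1−s), λ0 = ln 2/12 and λ1 = ln 2/24. The test rejects when 2·λ0·(total time) exceeds the 95th percentile of χ² on 2 × events degrees of freedom (53.38 for 19 events).

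- *Literal rule.* All 19 exits are events, with hazard λ1/(1−s). The ratio to λ0 is 0.5/(1−s), and power = P(χ²₃₈ > 53.38 × ratio).
- *Censoring.* Expected progression events are 19(1−s); power is by simulation with the same test.

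| s | Hazard ratio to benchmark, literal | Median, literal (24 × (1−s)) | Power, literal | Progression events if censored | Power, censored |
|---|---|---|---|---|---|
| 10% | 0.556 | 21.6 weeks | 83% | 17.1 | 90% |
| 20% | 0.625 | 19.2 weeks | 68% | 15.2 | 88% |
| 30% | 0.714 | 16.8 weeks | 46% | 13.3 | 85% |

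The differences are about 7, 20 and 39 points. With censoring the underlying median stays at 24 weeks.

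**Direction.** If the true median is 12 weeks and exits occur at the same weekly rate r·λ1, the literal rule rejects with probability P(χ²₃₈ > 53.38 × (1 + r/2)), about 2.8, 1.3 and 0.4%. Censoring gives about 5% in simulation. The literal rule is conservative.

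**Dependence on the benchmark.** If the historical 12 weeks already contained the same share of such events, the hazard ratio is 0.5 again and power under the literal rule is 91.6%: no cost. If instead it contained them at the same weekly rate, so that a progression-only median of 12 weeks would be compared on the mixed endpoint, the ratio is (1+r)/(2+r) = 0.526, 0.556 and 0.588. Power is then 88, 83 and 77%, a cost of about 2, 5 and 9 points against censoring.

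**What is left out, and why.** Dating progression on the 8-weekly scans while testing against a continuous 12-week benchmark gives a test that is not at 5%. With a true median of 12 weeks it rejects about 21 to 23% of the time with censoring and 6 to 17% under the literal rule. Power from that set-up cannot be read as power at 5%, so none is given. The effect on the futility look is not quantified either.

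**The case against.** The best counter-argument is grammatical. The preceding sentence in section 7.1 defines the event as progression, and the fallback speaks of the date of this event. Read so, it supplies a date for progression and adds neither death nor drug stop to the list of events. Section 2.2 and the stated reason for TTP support that reading. This stands as a plausible account of the intention, with no cost attached. It does not settle the matter: the limit is not written down, and a TTP censoring rule would still be missing.

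Second, the drug-stop route is partly covered. Section 5.4 continues imaging until progression, death, withdrawal of consent, end of study or new treatment, and section 6.2 asks for every effort to document progression. This also stands; deaths between scans are the more exposed case. Section 11.1 also confines the analysis set to patients with two cycles and a week-8 assessment and replaces those not evaluable, which would remove many early exits.

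Third, the literal rule is conservative and censoring gives up some of that protection. This is correct. A reader might infer that the sentence could manufacture a positive result; the arithmetic shows the opposite.

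A reader might also infer that the plan does count every death and every discontinuation as progression. The text permits that for patients who could not be assessed, but does not say it, and the dating-only reading remains open.

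**Conclusion.** The ambiguity in the primary endpoint and the absence of a TTP censoring rule are established by the text. The point should be fixed; the size of its effect is conditional. On the dating-only reading the cost is zero. On the literal reading it is about 7, 20 or 39 points of power at assumed shares of 10, 20 or 30%, with none to about 9 points remaining if the benchmark carried the same kind of events. These figures rest on exponential times, independent exits and continuous observation. They ignore the futility look and the week-8 filter, and are not estimates of this trial's power.

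It would be tempting to conclude that the trial is underpowered or that the historical comparison is invalid. The documents support neither: they give no share of non-progression exits and do not say how the cited trials scored deaths and drug stops. The supported conclusion is a risk of a missed benefit and of an endpoint that is not TTP as section 2.2 defines it.

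**What to change.** Use one definition in sections 2.2 and 7.1: first progression by RECIST, or clinical progression recorded by the investigator, at its recorded date. Then:

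- Confine the last-dose or death date to patients already judged to have progressed whose progression date could not be established by imaging, and say which of the two dates applies.
- Censor patients who die without progression, or who stop drug and are not scanned again, at the last adequate tumour assessment. Patients still being scanned after stopping drug remain at risk.
- State whether symptomatic deterioration in section 6.2 counts as clinical progression.
- Report PFS and the current last-dose/death rule as sensitivity analyses.

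The cost is wording in sections 2.2, 6.2 and 7.1, settled before any event is counted. The statistical price is fewer TTP events (about 17, 15 or 13 from 19 patients at the assumed shares), censoring that may be informative and can bias TTP upward, and some lost conservatism. That is why the two sensitivity analyses should accompany the primary result.
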